- i. Study procedures cannot be performed before the subject signs the ICF. Once the ICF is signed at the screening visit, sites should consider obtaining a medical history, vital signs and physical examination, and other per protocol screening visit investigations such as blood tests, ECG, and chest x-ray (if required), giving the subject the electronic study diary and training on the diary, and also scheduling the screening ileocolonoscopy and Week 0 visit. Sites should consider the turnaround time for the centrally read endoscopy result when scheduling the ileocolonoscopy and Week 0 visits.
- ii. The study diary requirements for the calculation of CDAI/PRO2 are outlined in [Section 9.1](#). In order to ensure that a CDAI score can be determined, sites should consider periodically confirming that subjects are successfully entering and uploading daily diary data.
- iii. Sites should check the results of screening investigations to confirm that a subject remains potentially eligible for inclusion before they commence bowel preparation for the screening ileocolonoscopy.
- iv. Once the screening ileocolonoscopy is performed, subjects should be randomized within 14 days.

In order to be eligible for randomization, subjects must have had an inadequate response, LOR, or intolerance to a standard treatment course of 1 or more of the following medications, as outlined in Inclusion Criterion 2)g):

- i. Oral 5-ASAs, oral corticosteroids, intravenous (IV) corticosteroids, or immunomodulators, and/or
- ii. Infliximab, adalimumab, certolizumab pegol, vedolizumab, ustekinumab, or natalizumab.

 The prior medication failure or intolerance used to qualify a subject for Inclusion Criterion 2)g) must be recorded in source documents.

The medications outlined in [APPENDIX 7](#) are subject to a washout period prior to the day of randomization (Week 0). These medications include immunomodulators (eg, methotrexate [MTX], 5-azathioprine [AZA], 6-mercaptopurine [6-MP]) and biologic medications (eg, infliximab, adalimumab, certolizumab pegol, vedolizumab, natalizumab, and ustekinumab). In order to be eligible for randomization, subjects taking the medications listed in [APPENDIX 7](#) must discontinue those medications prior to randomization and comply with washout periods listed in [APPENDIX 7](#).

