6.1 Inclusion Criteria

1) Signed Written Informed Consent

- a) Willing to participate in the study and sign the ICF.
- b) Willing and able to complete all study-specific procedures and visits.

2) Type of Subject and Target Disease Characteristics

- a) Not applicable per Global Revised Protocol v3.0
- b) Not applicable per Global Revised Protocol v3.0
- c) Not applicable per Global Revised Protocol v3.0
- d) Not applicable per Global Revised Protocol v3.0
- e) Documented diagnosis of CD for at least 3 months prior to screening, including ileal, colonic, or ileo-colonic disease distribution, confirmed by:
 - ◆ Source: Medical records with report of a colonoscopy with ileal intubation (ileocolonoscopy), which shows features consistent with CD, as determined by the procedure performing physician, AND
 - ◆ Source: Medical record documentation of a histopathology report showing features consistent with CD, as determined by the local pathologist.

Note: If a histopathology report is not available, histologic samples can be obtained at the screening endoscopy and sent to a local laboratory to confirm diagnosis of CD before proceeding to randomization. The screening endoscopy must show features consistent with CD.

- f) Must have active moderate to severe CD, as defined by:
 - CDAI score of 220 to 450 AND
 - PRO2: Average daily score for abdominal pain ≥ 2 OR average daily number of very soft (loose) or liquid (watery) stools (BSS Type 6 or 7 only; XXXXXXXXXX ≥ 4 , (see [Section 9.1](#)), AND
 - Evidence of active inflammation in at least 1 of the 5 ileocolonic segments (based on central reading) with total SES-CD ≥ 6 or SES-CD ≥ 4 if only isolated ileitis is present on baseline endoscopy

- g) Must have had an inadequate response, LOR, or intolerance to a standard treatment course of 1 or more of the following medications as below:
- Oral 5-ASAs: (eg, mesalamine, sulfasalazine, olsalazine, balsalazine) at or above the approved label dose (or per local standard of care) for induction therapy for at least 6 weeks
 - Oral corticosteroids: Prednisone \geq 40 mg/day or equivalent for 2 weeks, or 2 failed attempts to taper oral corticosteroids below prednisone or equivalent 10 mg daily, or a relapse within 3 months of discontinuing corticosteroids
 - Intravenous (IV) corticosteroids: hydrocortisone \geq 400 mg/day or equivalent for at least 1 week

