 - Immunomodulators: AZA \geq 1.5 mg/kg/day, 6-MP \geq 0.75 mg/kg/day, MTX \geq 15 mg/week, or as per Institutional Practice/Country-approved label or guideline, for at least 12 weeks. At institutions that utilize thiopurine levels in clinical practice: AZA or 6-MP prescribed for at least 12 weeks with at least 1 demonstration of therapeutic thiopurine metabolite levels. Note: subjects with defined NUDT15 or TPMT mutations who experience intolerance to thiopurines at lower doses than those listed above may be eligible for this study. This should be discussed with the medical monitor on a case-by-case basis.
 - Biologics: (eg, infliximab, adalimumab, certolizumab pegol, vedolizumab, natalizumab, ustekinumab) [REDACTED] Subjects can be included if treatment with a biologic was stopped due to primary or secondary nonresponse, or were intolerant to treatment, [REDACTED].

3) Age and Reproductive Status

- a) Men and women aged 18 to 75 years inclusive at the time of screening
- b) Women of childbearing potential (WOCBP) must have a negative serum or urine pregnancy test (minimum sensitivity 25 IU/L or equivalent units of beta-human chorionic gonadotropin) within 24 hours prior to the start of study treatment.
- c) Women must not be breastfeeding
- d) Not applicable per Global Revised Protocol v3.0
- e) Not applicable per Global Revised Protocol v3.0
- f) Not applicable per Global Revised Protocol v3.0
- g) Not applicable per Global Revised Protocol v3.0
- h) Azoospermic males are exempt from contraceptive requirements. WOCBP who are continuously not heterosexually active are also exempt from contraceptive requirements, and still must undergo pregnancy testing as described in this section.
- i) Not applicable per Global Revised Protocol v3.0
- j) Not applicable per Global Revised Protocol v5.0
- k) Investigators shall counsel WOCBP and men who are sexually active with WOCBP on the importance of pregnancy prevention and the implications of an unexpected pregnancy. Investigators shall advise on the use of methods of contraception ([APPENDIX 5](#)).
- l) Male subjects should maintain their usual practice with regards to contraception (if any). However, no specific additional contraceptive measures are required.

- m) WOCBP must agree to at least an acceptable, less than highly effective means of contraception (see [APPENDIX 5](#)) for the duration of treatment with study treatment(s) (BMS-986165 or placebo).

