 - Administration of a live vaccine within 90 days before the first dose of study treatment administration. Heat-killed, or otherwise inactivated, protein or subunit vaccines (eg, influenza and pneumococcal vaccines), nucleic acid vaccines that do not encode potentially infectious virus, and replication-incompetent recombinant vector vaccines may be received at any time on study. Furthermore, live vaccines should not be used during the study and within the 2 months following last dose, and any other inactivated vaccines (eg, tetanus, etc.) should be used according to local guidelines during the treatment period.
 - Current or recent (within 3 months before the first dose) gastrointestinal disease, including gastrointestinal surgery, that could impact the absorption of study treatment, or current or recent (within 6 months before the first dose) gastrointestinal resections
- l) Drug or alcohol abuse, as determined by the investigator, within 6 months prior to Day 1 (Note: medical marijuana is not allowed)

3) Prior/Concomitant Therapy

- a) Inability to comply with restrictions and prohibited treatments, as listed in [Section 7.7](#)
- b) Not applicable per Global Revised Protocol v3.0
- c) Not applicable per Global Revised Protocol v3.0
- d) Not applicable per Global Revised Protocol v5.0

- e) Inadequate response or LOR to medications that target the same pathway as BMS-986165 such as anti-12/23p40 antibodies (eg, briakinumab) or anti-IL-23p19 antibodies (eg, guselkumab, risankizumab, tildrakizumab, brazikumab [MEDI2070], and mirikizumab [LY3074828]). However, subjects who have been exposed to the medications listed above but have not had a treatment failure (ie, an inadequate response or LOR) may be eligible for inclusion. Similarly, subjects who have experienced intolerance to the medications listed above (eg, an infusion reaction) without a treatment failure may be eligible for inclusion.

4) Physical and Laboratory Test Findings

- a) Evidence of organ dysfunction or any clinically significant deviation from normal in physical examinations, vital signs, ECG, chest x-ray, or clinical laboratory determinations beyond what is consistent with the target population
- b) Not applicable per Global Revised Protocol v3.0
- c) Not applicable per Global Revised Protocol v3.0
- d) Clinically significant abnormalities on chest x-ray or ECG
- e) Clinically significant abnormalities in laboratory testing including:

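### Does exclusion 3)e bar ustekinumab failures whom inclusion 2)g lets in?

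*Combined protocol and SAP*

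**What the plan says.** Three places in the protocol bear on prior ustekinumab failure.

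- **Section 6.2, exclusion 3)e** excludes "Inadequate response or LOR to medications that target the same pathway as BMS-986165 such as anti-12/23p40 antibodies (eg, briakinumab") or anti-IL-23p19 antibodies, for which five examples are given. Two groups are let back in: "subjects who have been exposed to the medications listed above but have not had a treatment failure", and "subjects who have experienced intolerance to the medications listed above (eg, an infusion reaction) without a treatment failure may be eligible for inclusion". Ustekinumab is not mentioned, and no redaction shows in this criterion.
- **Section 6.1, inclusion 2)g** has the stem "Must have had an inadequate response, LOR, or intolerance to a standard treatment course of 1 or more of the following medications as below". Its last item reads "Biologics: (eg, infliximab, adalimumab, certolizumab pegol, vedolizumab, natalizumab, ustekinumab"), and goes on: "Subjects can be included if treatment with a biologic was stopped due to primary or secondary nonresponse". Text is blacked out on both sides of that last sentence.
- **Section 5.1.1** restates the requirement: "subjects must have had an inadequate response, LOR, or intolerance to a standard treatment course of 1 or more of the following medications", with the biologic list "Infliximab, adalimumab, certolizumab pegol, vedolizumab, ustekinumab, or natalizumab". The Synopsis has a similar list.

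The Synopsis background and Section 3.1 both describe ustekinumab as acting on IL-12/23p40. Section 6 requires the criteria of 6.1 and 6.2 to be met together, and Section 6.3 has eligibility confirmed again before randomization.

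**The concern.** The bar in 3)e is defined by pathway and illustrated by examples, so leaving a drug out of the examples does not take it out of the class. On the protocol's own description, ustekinumab belongs there. The only exceptions are for patients without treatment failure. A patient who stopped ustekinumab for nonresponse or loss of response therefore seems to satisfy 2)g and to be stopped by 3)e.

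If sites took 3)e literally, they would screen-fail patients whom the inclusion list appears to welcome. If some sites randomized such patients and others did not, the eligibility-deviation count would depend on how each site read the criterion. The stake is the make-up of the screened-in population and the deviation listing.

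**Working it through.** No figure in the plan depends on this point, so the check is a comparison of texts.

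**Step 1: where the readings differ.** Take the four possible ustekinumab histories and apply 2)g, then 3)e under each reading.

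| Ustekinumab history | Meets 2)g through ustekinumab | Barred if 3)e is an open class | Barred if 3)e covers only named agents |
|---|---|---|---|
| Primary nonresponse | yes | yes | no |
| Loss of response | yes | yes | no |
| Intolerance, no failure | yes | no | no |
| Exposure, no failure | no | no | no |

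The readings part in 2 of 4 rows. These are categories, not patients; the documents do not say how many subjects fall in each.

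**Step 2: is there a formal contradiction?** No. Inclusion 2)g is a necessary condition, and exclusions ordinarily remove people who satisfy an inclusion item. A patient who failed both infliximab and risankizumab meets 2)g and is barred by 3)e, with nothing inconsistent in that. Even on the strict reading, ustekinumab could stay in the 2)g list for patients who were only intolerant of it. What exists is an ambiguity about the reach of 3)e.

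**Step 3: which reading does the document support?**

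- The agents named in 3)e are 1 anti-p40 (briakinumab) plus 5 anti-p19 (guselkumab, risankizumab, tildrakizumab, brazikumab, mirikizumab), 6 in all. Ustekinumab is 0 of 6, although it is named in 2)g, Sections 5.1.1, 6.3 and 7.7.2, and Appendix 7.
- Both exceptions in 3)e point back to medications already listed, which treats what precedes as a list.
- Inclusion 2)g names ustekinumab specifically and accepts nonresponse to a biologic; 3)e speaks only of a general class.
- The Document History and Appendix 21 state that Amendment 04 removed the exclusion of ustekinumab inadequate response or loss of response. Appendix 21 lists Section 6.2 among the sections changed and says that 3)e was created from the former 3)d. This is used only as evidence of intent; a difference between an amendment history and current text would not be an error in itself.

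**Step 4: could hidden text settle it?** Possibly. Appendix 21 says the ustekinumab change touched Sections 5.1.1, 6.1, 6.2 and 7.7.1 and one further section whose name is redacted. The biologics item of 2)g is partly blacked out and item 2 of Section 7.7.1 is blank in the public copy. Sites work from the full text.

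**Step 5: does it reach the analysis?** Section 10.2 defines the Full Analysis Set as all randomized subjects, grouped as randomized, and makes it the primary efficacy population. A deviation label does not remove anyone from it. Eligibility is decided before randomization, so either reading applies alike to all three arms. The 0.025 allotted to each dose comparison does not depend on it.

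**The case for a change.** The best case for a change is that sites apply the criteria and not the amendment history, and that this protocol writes exceptions out when it wants them. Exclusion 1)s spells out one for local stem cell therapy and 4)e one for Gilbert's syndrome, both added or clarified at Amendment 04. Exclusion 3)e came from the same amendment, so it is where a ustekinumab exception would be expected. The reference back to listed medications occurs only in the exceptions, not in the bar, and the p40 class is itself among the things listed. A clarification elsewhere would leave the literal wording of 3)e as it is. The remedy would be a few words, and Amendment 05 shows that the sponsor has used an administrative letter for the numbering of inclusion criterion 2.

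Much of this stands. The wording is open, no carve-out is visible in 3)e, and a strictly literal site could screen-fail a patient the sponsor meant to admit. What does not follow is a consequence for the trial's conclusions: no bias, loss of power or alpha error is shown, and no count of affected patients can be given. The literal reading also has to set aside the specific mention in 2)g, the absence of ustekinumab from the examples and the stated purpose of the amendment.

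**Conclusion.** This is a minor drafting ambiguity, and it calls for no change to the plan. It affects 2 of 4 ustekinumab histories, for an unknown number of patients, and touches only who is screened in and how a deviation might be labelled. The current criteria read together, with the amendment history as a guide to intent, give a coherent reading that sites and analysts can be expected to adopt. The primary comparison rests on all randomized subjects under either reading.

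This assumes that the visible text of 3)e is complete and that the redacted passages do not say the reverse. Some analysis populations in Section 10.2 are redacted, so an effect on a secondary set that drops eligibility deviations cannot be excluded; the primary set is not affected. Whether prior ustekinumab failures ought clinically to be enrolled is not judged here. If the sponsor revises 3)e for another reason, an explicit statement on ustekinumab that reconciles it with 2)g would be a courtesy to sites.

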6.3 Randomization Criteria

Eligible subjects must meet the following criteria on Day 1 before randomization and the first dose:

- 1) The subject continues to satisfy all eligibility criteria.
- 2) If no previous confirmation of diagnosis is available or if previous diagnosis is not deemed conclusive, at time of baseline endoscopy, histology must be performed and read locally to confirm diagnosis of CD.
- 3) Previous therapy must follow the rules outlined below:
 - a) 5-ASAs must be at stable doses for at least 2 weeks prior to the first dose of study treatment on Day 1 of the Induction Period.
 - b) Probiotics must be at stable doses for at least 2 weeks prior to the first dose of study treatment on Day 1 of the Induction Period.
 - c) CD-related antibiotics (ciprofloxacin, metronidazole, etc.) must be at stable doses for at least 2 weeks prior to the first dose of study treatment on Day 1 of the Induction Period.
 - d) Corticosteroids:
 - Prednisone \leq 20 mg QD PO (or equivalent) or ileal-release budesonide \leq 9 mg QD PO (eg, Entocort® EC) must be stable for at least 2 weeks prior to randomization.
 - Use of IV corticosteroid is prohibited within 14 days prior to or during the Screening Period.
 - e) Prior exposure to the immunomodulators 6-MP, AZA, and MTX is permitted, but these agents must be discontinued for at least 4 weeks prior to the first dose of study treatment on Day 1 of the Induction Period. Treatment with cyclosporine, mycophenolate mofetil, leflunomide, tacrolimus, JAK inhibitors, or IFN must be discontinued prior to the first dose of study treatment on Day 1 of the Induction Period as described in [APPENDIX 7](#).
 - f) The washout period for biologics is discussed in [Section 5.1.1](#) and [APPENDIX 7](#). The washout period for infliximab, adalimumab or certolizumab pegol may be waived for subjects with an undetectable drug level on a TDM assay performed in routine clinical practice, or in screening. The washout period for subjects who have received vedolizumab maintenance therapy for > 14 weeks or ustekinumab therapy for > 12 weeks may similarly be waived, if a TDM assay shows undetectable drug levels on a TDM assay.

6.4 Lifestyle Restrictions

No restrictions are required.

Study treatment may be taken without regard to meals. However, subjects are required to fast for a minimum of 10 hours before visits on which fasting lipid and fasting glucose samples will be drawn (at 2 of these visits [Days 1 and 85], [REDACTED]

6.5 Screen Failures

Screen failures are defined as subjects who consent to participate in the clinical study but who are not subsequently randomized in the study. A minimal set of screen failure information is required to ensure transparent reporting of screen failure subjects, to meet the Consolidated Standards of Reporting Trials publishing requirements, and to respond to queries from regulatory authorities. Minimal information includes date of consent, demography, screen failure details, eligibility criteria, and any SAEs.

The study permits the rescreening of a subject who has been deemed as ineligible (screen failure) during the Screening Period (ie, the subject has not been randomized/has not been treated). Subjects who were screen-failed due to *C. difficile* infection must be adequately treated and subsequently test negative for *C. difficile*. The subject must be re-consented (ie, re-signing of the ICF), and rescreened (if outside the 28-day Screening Period window). Only 1 re-enrollment per subject is permissible.

6.5.1 Retesting During the Screening Period; Rescreening

For laboratory parameters and/or assessments (Table 1) that initially do not meet eligibility requirements, a single retest within the 28-day Screening Period is permitted in an effort to find all possible well-qualified subjects, unless otherwise noted. Consultation with the medical monitor may be needed to identify whether repeat testing of any particular parameter is clinically relevant.

The study permits the rescreening (after the end of the initial 4-week Screening Period) of a subject who discontinues the study as a pretreatment failure (ie, the subject fails screening or randomization and has not been treated) or if they have experienced an infection with *C. difficile* and were adequately treated, and subsequently test negative for *C. difficile* (see APPENDIX 20). The subject must be re-consented and will be assigned a new identification number, and a full screening visit must be performed again.

A subject can only be rescreened 1 time (ie, if the subject fails 1 rescreening attempt, no additional rescreening is allowed). Duration of existing treatments and required discontinuation periods shall be considered relative to the given screening visit and/or randomization.

Subjects who were previously randomized in IM011023 are not eligible for rescreening, even if they did not receive a dose of study treatment.

If subjects test positive for *C. difficile* (see APPENDIX 20), they can be rescreened 30 days after completing a full course of standard treatment for *C. difficile* colitis and subsequently test negative for *C. difficile*.

The most current result prior to randomization is the value by which study inclusion will be assessed, as it represents the subject's most current clinical state.

[figure not shown]
7 TREATMENT

Study treatment is defined as any investigational treatment, marketed product, placebo, or medical device intended to be administered to a study subject according to the study randomization or treatment allocation.

Study treatment includes IP/investigational medicinal product (IMP) and consists of placebo and BMS-986165. Information about the pharmacology and previous experience with BMS-986165 is provided in [Section 3.1.1](#) and [Section 3.1.2](#).

An IP, also known as IMP in some regions, is defined as a pharmaceutical form of an active substance or placebo being tested or used as a reference in a clinical study, including products already with a marketing authorization but used or assembled (formulated or packaged) differently than the authorized form, or used for an unauthorized indication, or when used to gain further information about the authorized form.

Other medications used as support or escape medication for preventative, diagnostic, or therapeutic reasons, as components of the standard of care for a given diagnosis, may be considered as non-IPs.

7.1 Treatments Administered

During the Induction Period, subjects will take BMS-986165 6 mg BID or 3 mg BID or placebo BID over 12 weeks ([Section 5.1.2](#)). For each dose level of BMS-986165 or placebo, capsules are taken BID (ie, once in the morning and once in the evening). [REDACTED]

Study treatment for subjects with no response or who have lost response, and enter into the open-label portion of the study will be supplied with the 3 mg hard gelatin capsules. [REDACTED]

[figure not shown]
If a subject forgets a dose, but remembers within 4 hours of the expected dose, the dose should be taken. If it is past 4 hours, that dose should be missed, and the next expected dose should be taken at the usual time.

Study treatment will be administered in the Maintenance Period, as described in [Section 5.1.3](#) and illustrated in [Figure 1](#).

Clinical Responders at Week 12: Subjects who achieve a clinical response (a reduction from baseline in the CDAI score of ≥ 100 points or a total CDAI score < 150) at Week 12 may be eligible to enter the double-blind and placebo-controlled Maintenance Period. During the Maintenance Period, subjects will take the same blinded study treatment dose level (BMS-986165 6 mg BID or 3 mg BID or placebo BID) that was assigned during the Induction Period. Subjects who were randomized to the BMS-986165 12 mg QD PO study arm when Protocol v1.0 (27-Mar-2018) or Protocol v2.0 (24-May-2018) were in effect who have not yet reached Week 12 will continue to receive blinded BMS-986165 12 mg QD for the Maintenance Period if they achieve a clinical response at Week 12.

Clinical Non-Responders at Week 12: Subjects who do not achieve a clinical response at Week 12 and who have an appropriate safety profile are eligible to switch to the BMS-986165 6 mg BID PO in the open-label study arm, regardless of the initial treatment regimen received during the 12-week Induction Period. Subjects who were randomized prior to when Protocol v1.0 (27-Mar-2018) or Protocol v2.0 (24-May-2018) were in effect and are currently receiving open-label BMS-986165 12 mg QD will continue on that dose until discontinuation.

At Week 26 of the Maintenance Period, the investigator will check if these subjects have achieved a clinical response (compared to Week 0). Subjects who achieve a clinical response at Week 26 (compared to Week 0) will continue on open-label treatment at the highest dose level (6 mg BID), or continue 12 mg QD if they were already receiving it. Subjects who do not achieve a clinical response at Week 26 (compared to Week 0) will be considered treatment failures and must permanently discontinue [REDACTED]

